Uncontrolled DM is associated with significant microvascular complications such as retinopathy, nephropathy and neuropathy; it can also result in macrovascular complications such as stroke and myocardial infarction.⁶ DM is considered a coronary heart disease risk equivalent, and its contribution to cardiovascular diseases (CVD) increases patient morbidity and mortality by as much as 60% in Singapore.^{7,8} Studies have shown that the prognosis for subjects with DM without prior CVD was worse than that for non-diabetic subjects with prior CVD.^{9,10} Therefore, in order to prevent and reduce the occurrence of short-term and long-term macrovascular and microvascular complications, a holistic management of DM should include close monitoring of patient's blood pressure (BP) and lipid profile in addition to good glycaemic control.

The management of DM and its associated co-morbidities can be complex, and often requires multiple medications along with strict lifestyle modifications.^{11,12} Since chronic diseases are lifelong and without cure, strict and continuous lifestyle modifications can be exhausting; and for most patients, pharmacotherapy becomes the mainstay of chronic disease management. However, with time, pill burden may increase, and medication adherence and drug interactions can become a problem for many patients with chronic diseases.^{13,14} In addition, limited physician-patient contact can result in suboptimal care as different aspects of DM care such as extraction of subjective data from a thorough interview with the patients, monitoring of objective data trends, drug optimization, medication tolerability, lifestyle modifications and accuracy in the use of medications and auxiliary devices cannot be addressed.^{13,15} Such situations may give rise to not only therapeutic failure but also potential drug-related adverse events or drug-drug interactions, which can increase the risk of drug-related mortality and morbidity.¹¹

Studies conducted in different countries have shown that due to the complex nature of the chronic disease state, a collaborative care model can be a more effective approach in managing patients with DM.^{11,14-16} In addition to physicians, such a collaborative effort often includes clinical pharmacists, nurses, dietitians and/or social workers. Care carried out by these experts in different aspects of DM has been found to yield positive treatment outcomes for patients.^{13,16,17}

In countries such as Singapore, Jordan, the United States, and Canada, the collaborative care model has been shown to optimize therapeutic outcomes of patients with DM as evidenced by improvements in surrogate markers such as HbA1c, BP, LDL and TG (Table 1).¹⁸⁻²¹ These studies had a follow-up period ranging from 3 to 9 months. Although the degree or level of improvements vary across countries, the collaborative care model has shown to improve clinical outcomes of patients with DM.

Author	Study	Country	Clinical Outcomes				Comments
(year)	Design		HbA1c	SBP	LDL	TG	
			(%)	(mm Hg)	(mmol/L)	(mmol/L)	
Siaw	Randomis	Singapore	INT: -	No	No	No	Treatment
MYL et	ed		0.3% at	significant	significant	significant	satisfaction and
al.	controlled		3-month	changes	changes	changes	distress were also
(2017) ¹⁸	trial		and -	over 6	over 6	over 6	assessed (better
			0.5% at	months	months	months	outcome in INT). INT
			6-month				also shown to
							significantly reduce
							direct medical costs
							as compared to UC.
Jarab AS	Randomiz	Jordan	INT: -	INT: -5.8;	INT: -0.6;	INT: -0.5;	Medication
et al.	ed		0.8; UC:	UC: +1.1	UC: No	UC: +0.2	adherence and self-
(2012) ¹⁹	controlled		+0.1		change		care techniques also
	trial						improved in INT.
Scott DM	Randomis	United	INT: -	INT: -3.4;	INT: -0.5;	NIL	Quality of life was
et al.	ed	States of	1.7; UC:	UC: +2.1	UC: -0.2		assessed using
$(206)^{20}$	controlled	America	-0.9				DQOL; some
	trial						components favour
							IN I but total scores
							were not significantly
							different between INI
	D. I. I.						
Katherine	Randomis	Canada	IN 1 : -	INT: -2.0;	IN1:-7.7;		DQLCLIQ and SF-36
$(2005)^{21}$	ea		0.29;	00: +7.0	UC: +1.6	+40.6;	Were assessed.
(2005)21	controlled					00:-0.9	
	unai		+0.72				such as global role
							impact health
							distross and social
							uisiress, and social
							significantly improved
							in INT
							IN INT.

Table [•]	1. Im	provements ir	Surrogate	Markers	from (Collaborative	Care Model
IUNIC			ounoguio	marker 5	in onit y	oonusorunve	

Abbreviations: INT, intervention; UC, usual care.

In addition, positive humanistic outcomes were also illustrated in studies that looked at the effectiveness of collaborative care in terms of patient quality of life and medication adherence. In one study, it was shown that there was a statistically significant increase in mean \pm standard deviation WB-Q12 scores (well-being) in the intervention group (21.9 \pm 6.8 to 23.4 \pm 6.8, p=0.04) but no change among controls at follow-up.¹³ Furthermore, the total mean \pm SD BMQ score (beliefs about medications and medication adherence) dropped from 3.89 \pm 1.78 to 2.74 \pm 1.39 in the intervention group and increased from 2.81 \pm 1.15 to 3.90 \pm 1.45 (p<.001) for the control group.¹³

Lastly, a collaborative care approach has demonstrated a reduction in overall health care costs for patients with DM.²² One study found that collaborative care was associated with a 62% decrease in the annual cost of treatment (\$107,939.99 vs. \$41,106.30 [U.S.]).²² Furthermore, after accounting for the additional cost of glucose monitoring (\$30,604), there was still 34% annual savings for patients.²²

Currently in Singapore, the effectiveness of the collaborative care model has only been evaluated prospectively for a duration of 6 months. The long-term impact of this care approach on the clinical, humanistic and economic outcomes have yet to be elucidated.

In summary, due to the complex nature and multifactorial causes of chronic diseases, healthcare systems around the globe face many challenges as they work to deliver effective chronic disease management. Evidence has shown that health care can be delivered more effectively and efficiently through a multidisciplinary team approach, in which providers are supported by experts from different disciplines, and as a result are better equipped with the necessary resources and knowledge to manage their patients' chronic diseases.¹⁸⁻²¹ With a diverse group of healthcare professionals on board, the healthcare team can ensure that their patients' treatment goals are attained in the short-term and maintained in the long-term.

Specific Aims and Objectives

The purpose of this study is to determine the effectiveness of the collaborative care model in Singapore in which clinical pharmacists, nurses and dietitians are active participants who collaborate with physicians in caring for patients with type 2 DM. Since type 2 DM is a cardiovascular risk equivalent, co-morbidities such as hypertension (HTN) and dyslipidaemia (DLP) will also be evaluated to assess the holistic care provided for our patients afflicted with these top chronic diseases in Singapore.

Specifically, this study aims to evaluate the long-term effectiveness and sustainability of an integrated collaborative care model comprising of a healthcare team (physician, clinical pharmacist, nurse, and/or dietitian) compared to the usual or conventional healthcare model (physician-centred care) mainly in the following outcomes (Table 2).

Types of Outcomes	Descriptions				
Clinical	• Glycated haemoglobin (HbA1c), systolic blood pressure (SBP), low density				
	lipoprotein (LDL), total cholesterol, high density lipoprotein (HDL) and fasting				
	triglyceride (TG) levels				
	 Incidence of minor and major hypoglycaemia 				
	 DM-related clinical visit and hospitalization 				
Humanistic	Health-related quality of life				
	Self-care management				
	Diabetes-related distress				
Economic	Cost effectiveness				
	Productivity				

Table 2. Outcome Measures for Proposed Study

The central hypothesis of this study is that patients with type 2 DM under the collaborative care model will have greater improvements in the clinical, humanistic and economic outcomes assessed than those under conventional care.

Data collection period:

12 March 2018 to 12 March 2020

Study Design and Methodology:

Study Design and Setting

This proposed project is a prospective, randomized controlled study to be conducted over a 12month period. This multi-centre study will be conducted in Bukit Batok and Choa Chu [name] Polyclinics.

Study Participants

Patients aged \geq 21 years with Type 2 DM (HbA1c > 7%) and polypharmacy (\geq 5 medications) will be eligible for this study. Patients with Type 1 DM or who are unable to communicate independently in English, Chinese or Malay will be excluded from this study.

Procedures

Eligible patients will be screened and identified by research assistants of this study. Upon agreeing to participate in the study and signing of the informed consent, the patients will be randomised to either the control or intervention group using a random number generator or an equivalent by the research assistants.

Patients randomly assigned to the usual or conventional care arm may be subject to as needed referral to the nurses for soft skill-related DM counselling and dietitian for diet control, at the discretion of the physician. These patients may be seen by different physicians at each visit, and pharmacists will not be involved in drug optimization except for dispensing.

Patients randomly assigned to the collaborative care arm will see a healthcare team comprising clinical pharmacists in addition to physicians, nurses and dietitians. The clinical interventions carried out by the clinical pharmacist include but are not limited to counselling patients about drug therapy, performing simple physical assessments, ordering pertinent follow-up visits and laboratory tests on behalf of the physicians, and initiating, titrating, and terminating medications per the NHG Hypertension, Diabetes, Lipids Clinic (HDL-C) Protocol and under the supervision of the physicians as appropriate. The supervision is usually in the endorsement of prescriptions prepared by clinical pharmacists. In addition, the clinical pharmacist will serve as a bridge between patients and physicians to increase communication, and patients will need to be seen by physicians at least every four months. As needed, referrals to nurses and dieticians will also be actively made by the clinical pharmacist and vice versa. The clinical pharmacist will schedule clinic appointments approximately every four to six weeks in the 12-month interventional period. If the patient's DM is well-controlled, i.e. with stable improvements in clinical measures, the clinical pharmacist may replace one or two clinic visits with telephone counselling at his/her discretion. All clinical pharmacists are board-certified pharmacotherapy specialists and/or board-certified ambulatory care pharmacist, and they have undergone the 3-month internal rotational endocrinology training held at Tan Tock Seng Hospital, comprising preceptors who are endocrinologists, senior clinical pharmacists, diabetes nurse educators, dietitian, and podiatrist, similar to the previous study conducted.¹⁸

Data Collection:

The types of outcome measures and period of assessment are summarized in Table 3 below. Patient demographics, past medical history, and current medication use for both control and intervention group will be collected at enrolment. Serum creatinine level will also be followed up at every 6-month period to ensure that any diabetic complications are not due to change in organ function over time.

Outcomes	Parameters	Time Period			
1. Clinical outcomes	Treatment goal	Baseline [*]	6-month	12-month	
1.1 HbA1c	≤ 7%	\checkmark		\checkmark	
1.2 SBP	< 130 mm Hg	\checkmark			
1.3 LDL	< 2.6 mmol/L	\checkmark			
1.4 HDL	≥ 1.0 mmol/L	\checkmark			
1.5 Total cholesterol	< 5.2 mmol/L	\checkmark			
1.6 TG	< 2.3 mmol/L	\checkmark		\checkmark	
1.7 Self-reported incidence of minor	N/A	\ √		\checkmark	
and major hypoglycaemia					
1.8 DM-related clinic visit and	N/A	-	\checkmark		
hospitalization					
2. Humanistic outcomes	Measurement	Baseline [*]	6-month	12-month	
	instrument				
2.1 Health-related quality of life	EQ-5D-5L, ADDQoL ²³	\checkmark		\checkmark	
2.2 Self-care management	SDSCA ²⁴	\checkmark		\checkmark	
2.3 Diabetes-related distress	PAID ²⁵	\checkmark		\checkmark	
3. Economic outcomes	Type of costs	Baseline [*]	6-month	12-month	
3.1 Costs	Direct costs	-			
3.2 Productivity	Indirect costs (WPAI-GH)	-			

Table 3. Summary of Outcome Measures

 $\sqrt{}$: to be measured

*Baseline refers to any time within the past 6 months prior to recruitment

Abbreviations: HbA1c, glycated haemoglobin; SBP, systolic blood pressure; LDL, low-density lipoprotein; HDL, high-density lipoprotein; TG, triglyceride; DM, diabetes mellitus; EQ-5D-5L, EuroQoL 5-dimension 5-level; ADDQoL, Audit of Diabetes-Dependent Quality of Life; SDSCA, Summary of Self Care Activities; PAID, Problem Areas in Diabetes; WPAI-GH, Work Productivity Activity Impairment-Global Health.

Clinical Outcomes

The main clinical parameters to be collected include HbA1c, SBP, total cholesterol, LDL, HDL, and TG. These short-term surrogate markers are predictive of the development of long-term DM-related complications. In addition, total cholesterol and other lipid parameters allow for estimation of cardiovascular risk. While several laboratory measures of glycemic levels are available, HbA1c will be used in this study as it is a recommended and reliable index of mean glycemic control over three months. Other outcome measures include: 1) incidence of minor and major hypoglycemia reported by patients, 2) frequency of DM-related clinic visits (by physician, pharmacist, nurses, dietitians) as indicated on patients' appointment card and hospitalizations. Minor hypoglycemic events are defined as blood glucose of < 4.0 mmol/L or signs and symptoms with known precipitating causes such as irregular eating habits, increased daily activity or other attributes that can be modified. The minor hypoglycemic event should allow the patient to recover quickly with or without the ingestion of fast-acting glucose. Major hypoglycemic events are defined as any hypoglycemic symptoms, regardless of frequency, which require help from another person. The clinical information and laboratory values will be collected from the clinical databases available at the study sites, patient case notes, and patient self-reported questionnaires at baseline, at 6- and 12-month during the study period. Baseline laboratory values will be collected at enrolment. If values are not available at enrolment, the most recent value available within the 6 months preceding enrolment will be recorded.

Humanistic Outcomes

Health-related quality of life (HRQoL) will be assessed using Research Assistant-administered questionnaires at baseline and as close to the 6-month and 12-month follow-ups as possible. The HRQoL measures will include a generic measure, EQ-5D-5L, and a DM-specific measure, the Audit of Diabetes Dependent Quality of Life (ADDQoL), and Problem Areas in Diabetes (PAID). Self-care management capabilities of patients will be assessed by the Summary of Diabetes Self-Care Activities Measure (SDSCA).

Economic Outcomes

The economic evaluation will be conducted from an institutional perspective. Direct healthcare costs will be estimated over 12 months. The direct costs will include physicians' consultation fees, laboratory and procedures, medication costs, DM-related hospitalization, and DM-related A&E visits.

Number of Subjects to be enrolled:

A 12-month study conducted in the United States of America involving the collaborative care model reported an effect size of 0.4.²⁰ With an allocation ratio of 1:1 into the intervention or control arms, approximately 125 patients are needed in each arm, to obtain a statistical power of 80% (two-sided Type I error rate = 0.05) and after taking into account a 20% dropout rate. As such, 250 patients will be needed to assess the effectiveness of a collaborative care model versus the usual model of care in the polyclinics.

Data source:

Clinical data will be collected from patient electronic case notes, prescription records accessed from CPSS2 and iPharm and investigation results from the electronic laboratory module in CPSS2. Humanistic data and incidence of hypoglycaemia will be elucidated through participant's self-reported questionnaires. Cost data will be obtained from the respective institution financial databases.

Data Analysis:

Descriptive analyses will be performed on all variables. The differences in the improvement of clinical and patient-reported outcomes will be examined between the two groups using the Student's t test or Wilcoxon rank-sum test as appropriate. Categorical data between the two study groups will be analyzed using the Chi-square test for independence or Fisher's exact test when expected cell size is less than 5. Pearson's product-moment correlation will be used to examine correlations between continuous variables such as HbA1c and HRQoL scores. Baseline factors that are significant in the bivariate analysis will be included in a multiple linear regression model to investigate the unique impact of the intervention on and the unique association of individual factors with each outcome score while adjusting for other covariates. The level of Type I error rate will be set at P < 0.05.

The sum of the costs incurred will be compared between the two groups using the Wilcoxon rank-sum test as the cost data are not expected to be normally distributed. General linear models with a log-link to the gamma distribution will be used to conduct multivariate analysis of costs between the groups. Gamma distributions are well suited for cost data since it a right-

skewed distribution. A cost-effectiveness analysis will be performed in which the effectiveness is defined by reduction in HbA1c between baseline and the 12-month follow-up. The incremental cost-effectiveness ratio will be calculated in which the difference in total costs between two groups is divided by the difference in the reduction in HbA1c between the two groups. Sensitivity analysis will be conducted to evaluate the influence of uncertainties in the variables and assumptions employed on the analysis results.

Data Entry and Storage:

All research-related electronic data collected will be de-identified, coded and entered in Microsoft Excel spreadsheet that will be password-protected and will be stored together with research-related paper documents in the investigators office at the National University of Singapore Department of Pharmacy, Faculty of Science. All patient information will be kept strictly confidential, following the policies of the study institution(s) involved. For hardcopy data, they will be stored in designated locked cabinet(s) or room(s) that are accessible to authorized study personnel only. For electronic data, they will be stored on in a secured computer that is password-protected. The databases will not contain subject identifiers and the data linking subject identifiers and the subject identification codes will be stored separately. These documents will be retained for a minimum of three years after study completion or as per institutional policies.

Confidentiality of Data and patient Records:

Investigators in this study will have access to all research-related data on a need-to-know basis or as per institutional policies. Collaborators in this study will only have access to researchrelated data that has been coded and has no patient related identifier. Only the principal investigators and co-investigators or collaborators will have access to the data in the excel spreadsheet. There will not be any sharing or releasing of raw data to any other persons.

Publication:

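### Clinic-visit frequency is taken from the patient's appointment card, a source absent from the protocol's general source lists; if the card shows bookings, the miscount falls mainly on the collaborative arm

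*Protocol*

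**What the plan says.** DM-related visits are a listed clinical outcome (Protocol, Table 2 and Table 3 item 1.8). The Clinical Outcomes section places them among the other outcome measures, after the laboratory and blood-pressure parameters, and ties them to a source: "frequency of DM-related clinic visits (by physician, pharmacist, nurses, dietitians) as indicated on patients' appointment card and hospitalizations".

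Two general statements on sources do not mention the card. Later in Clinical Outcomes: "The clinical information and laboratory values will be collected from the clinical databases available at the study sites, patient case notes, and patient self-reported questionnaires". Under Data source: "Clinical data will be collected from patient electronic case notes, prescription records accessed from CPSS2 and iPharm", together with the electronic laboratory module.

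The Procedures section sets a different contact pattern in each arm. In the collaborative arm, "The clinical pharmacist will schedule clinic appointments approximately every four to six weeks in the 12-month interventional period". If diabetes is well controlled there, "the clinical pharmacist may replace one or two clinic visits with telephone counselling at his/her discretion". In usual care, "pharmacists will not be involved in drug optimization except for dispensing", and neither a visit interval nor telephone replacement is described.

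The protocol does not describe what the card records. It gives no rule for missed appointments and does not say whether a telephone contact counts as a visit.

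**The concern.** The protocol fixes a source for this outcome that its own source lists leave out, so staff following different sentences could count the same patient differently. The card also looks like the weaker choice. In its ordinary sense it holds appointments made. Unless someone marks it at attendance or corrects it afterwards, it keeps appointments that were missed or turned into calls, and it omits attendances that were never booked.

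Such an error would not be balanced. One arm has a dense appointment schedule and the only described route from visit to call; the other has neither. Telephone replacement also depends on good control, so within the collaborative arm any error from calls would sit in the patients who are doing well. What is at stake is the between-arm comparison of visit frequency, and what a reader can learn from it about how much of the planned contact took place.

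**Working it through.** The protocol gives no visit count to reproduce. Its one computed figure is the sample size. An effect size of 0.4, 80% power and two-sided 0.05 need 99 per arm by the normal approximation, or 100 with the t correction; 99/0.8 = 124 and 100/0.8 = 125, against the stated 125. That figure reproduces and does not depend on the card.

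**Inputs from the protocol (Procedures)**
- Pharmacist appointment interval, collaborative arm: 4 to 6 weeks over 12 months.
- Telephone replacement: one or two visits, optional and only if well controlled. The range per patient is therefore 0 to 2.

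**Assumptions (not in the protocol)**
- The card is a pure booking record and is not amended when a visit becomes a call.
- No-show rate r: 10% to 20%, the same in both arms.
- Usual-care bookings: 3 to 4 a year.

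**Bookings.** B = 52/interval: 52/6 = 8.7 and 52/4 = 13 a year. One or two calls are between 1/13 = 8% and 2/8.7 = 23% of these.

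**Overcount.** With C visits replaced by calls, no-shows can occur only among the remaining B - C, so bookings not attended = C + r(B - C).

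| Setting | B | C | r | Overcount | As % of attended |
|---|---|---|---|---|---|
| Collaborative, lowest count | 8.67 | 0 | 10% | 0.87 | 0.87/7.80 = 11% |
| Collaborative, 6-weekly, two calls | 8.67 | 2 | 20% | 2 + 0.2 x 6.67 = 3.33 | 3.33/5.33 = 62.5% |
| Collaborative, highest count | 13 | 2 | 20% | 2 + 0.2 x 11 = 4.2 | 4.2/8.8 = 48% |
| Usual care, lowest | 3 | 0 | 10% | 0.3 | 0.3/2.7 = 11% |
| Usual care, highest | 4 | 0 | 20% | 0.8 | 0.8/3.2 = 25% |

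**Effect on the arm difference, same r in both arms.** The smallest exaggeration is 0.87 - 0.4 = 0.5 visits (r = 10%, no calls, 4 usual-care bookings). The largest is 4.2 - 0.6 = 3.6 visits (r = 20%, two calls, 3 usual-care bookings).

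**Could the contrast reverse?** Take the fewest attended pharmacist visits in the table, 5.33, and set them against 4 usual-care bookings all kept. The collaborative arm still has more.

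**Limits of the illustration.** The collaborative figures cover pharmacist appointments only. Physician visits at least every four months (12/4 = 3 a year), if booked separately, would add 0.1 x 3 = 0.3 to 0.2 x 3 = 0.6. Unbooked attendances work the other way and cannot be sized from the protocol, so these are gross overcounts, not net errors.

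**The case against.** The strongest reply is that the protocol never describes the card. It could be stamped at attendance, or corrected when a visit becomes a call, and a call planned in advance might never be written on it as a visit. A reader might infer that the card definitely shows bookings and that no-shows and calls will be counted as visits. The text does not support that; it is a condition on which the whole illustration rests.

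Second, the case notes and databases named elsewhere could supplement or check the card, so the statements may be complementary. That is possible, but the protocol does not say which governs, and the only source attached to this outcome is the card.

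Third, telephone replacement is optional and restricted to well-controlled patients, and entry requires HbA1c above 7%. Charging one or two calls to every patient would overstate the error, which is why the range starts at zero calls.

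Fourth, a reader might infer that resource use, costs or the cost-effectiveness ratio are biased. They are not shown to be: cost data come from institutional financial databases, and the ratio uses costs and HbA1c reduction. Nor does the protocol assign the visit count a role as the main measure of intervention delivery.

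Fifth, detailed counting rules may stand in an SAP or data-collection form that is not at hand. That is fair for the rules on missed and telephone appointments. It does not cover the choice of source, which the protocol itself states.

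**Conclusion.** The point holds as a minor one. The protocol names the appointment card as the source for a listed outcome, its general source statements omit the card, and a better source is already being accessed. If the card is an unamended booking record, the overcount is about 0.9 to 4.2 visits per collaborative patient-year against 0.3 to 0.8 in usual care. That rests on an assumed 10-20% no-show rate, 0 to 2 calls per patient and an assumed 3 to 4 usual-care bookings. If the card is reliably marked at attendance and corrected for calls, the overcount disappears, but the inconsistency between the source statements and the possible loss of unbooked attendances remain.

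The consequence is confined to the visit-frequency outcome. HbA1c, the humanistic outcomes, costs, the cost-effectiveness ratio and the sample size do not use the card. The greater number of visits in the collaborative arm, which the design itself imposes, would be exaggerated but not reversed under the illustrated assumptions.

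**What to change.** In Clinical Outcomes, replace the appointment card with attended DM-related visits by provider type (physician, pharmacist, nurse, dietitian), taken from the electronic case notes or clinical databases already accessed. Use the same 12 months from randomisation in both arms, include unbooked attendances, and report telephone contacts as a separate count. Align the sentence with the Data source section so that one source governs.

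The cost is one changed sentence and some extra record abstraction. The sites should first confirm that their records show attendance and separate telephone contacts from visits, because the protocol does not say that they do. Treatment, sample size and patient burden are unchanged.

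### The hypoglycaemia definitions leave a gap: a self-managed symptomatic event with no low glucose reading and no known modifiable cause is neither minor nor major

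*Protocol*

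**What the plan says.** Under Data Collection, Clinical Outcomes, the protocol defines both categories.

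- Minor, first limb: "Minor hypoglycemic events are defined as blood glucose of < 4.0 mmol/L or signs and symptoms".
- Minor, symptom limb in full: "signs and symptoms with known precipitating causes such as irregular eating habits, increased daily activity or other attributes that can be modified".
- Minor, recovery: "The minor hypoglycemic event should allow the patient to recover quickly with or without the ingestion of fast-acting glucose".
- Major: "Major hypoglycemic events are defined as any hypoglycemic symptoms, regardless of frequency, which require help from another person".

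No third or unclassified category is given. Hypoglycaemia is item 1.7 of Table 3, and the text lists it apart from the main clinical parameters.

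On the source of the data, the Data source section states: "Humanistic data and incidence of hypoglycaemia will be elucidated through participant's self-reported questionnaires". Clinical Outcomes places these among "patient self-reported questionnaires at baseline, at 6- and 12-month during the study period", with no difference between arms.

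Under Procedures, the collaborative arm's pharmacist has tasks that include "initiating, titrating, and terminating medications per the NHG Hypertension, Diabetes, Lipids Clinic (HDL-C) Protocol". Contact is frequent: "The clinical pharmacist will schedule clinic appointments approximately every four to six weeks in the 12-month interventional period". Usual care has nurse or dietitian referral as needed, at the physician's discretion. Under Patients Reimbursement, participants in either arm who complete the baseline questionnaires receive a glucometer and up to four bottles of 50 strips.

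**The concern.** A known, modifiable cause describes why an event happened, not whether it happened. Making it a condition for counting means that the least explained events drop out of the minor category. The major category does not pick them up, because the patient needed no help.

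This matters because the intervention alters glucose-lowering treatment in one arm, and hypoglycaemia is the listed outcome that most directly shows harm from doing so. An event that the definition excludes may never be recorded, and analysis cannot then recover it.

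There is a second, weaker worry. Whether a cause is known, and whether a reading was taken, may depend on how much counselling the patient has had, and the arms differ in that.

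**Working it through.** The protocol gives no figure on this point, so there is none to reproduce. The main check is a reading of the definitions; the arithmetic after it is an illustration.

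**Step 1: classify every symptomatic event.** The glucose limb is read in its natural sense, as needing no cause.

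| Help needed | Glucose below 4.0 mmol/L recorded | Known modifiable cause | Category |
|---|---|---|---|
| No | Yes | Yes or no | Minor |
| No | No | Yes | Minor |
| No | No | No | Neither |
| Yes | No | No | Major |
| Yes | No | Yes | Major; also fits minor if recovery is quick |
| Yes | Yes | Yes or no | Major; also fits minor if recovery is quick |

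The third row is the gap. If the phrase about causes is read as governing the glucose limb too, the gap widens to glucose-confirmed events with no known cause. An unassisted event with slow recovery also has no clear home, because of the recovery sentence.

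The last row is the overlap that matters most. It is confined to assisted events that resolve quickly, because the minor definition expects quick recovery. The row above it overlaps in the same way through the symptom limb.

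**Step 2: size under assumptions.** None of these inputs is in the documents.

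- s = share of unassisted events with symptoms and no reading: 0.3 to 0.5.
- p = probability that a modifiable cause is identified for such an event: 0.8 to 0.9 in the collaborative arm, 0.5 to 0.6 in usual care.

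Capture = (1 - s) + s × p. Uncounted share = s × (1 - p).

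| s | p = 0.9 | p = 0.8 | p = 0.6 | p = 0.5 |
|---|---|---|---|---|
| 0.3 | 0.97 | 0.94 | 0.88 | 0.85 |
| 0.5 | 0.95 | 0.90 | 0.80 | 0.75 |

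- Smallest uncounted share: 0.3 × 0.1 = 0.03. Largest: 0.5 × 0.5 = 0.25.
- Collaborative arm: 0.3 × 0.1 = 0.03 to 0.5 × 0.2 = 0.10. Usual care: 0.3 × 0.4 = 0.12 to 0.5 × 0.5 = 0.25.
- Apparent rate ratio when true rates are equal: lowest 0.94/0.88 = 1.07; highest 0.95/0.75 = 1.27.

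**Step 3: remove the arm difference.** With the same s and p in both arms the ratio is 1, but s × (1 - p) of events are still lost. The undercount does not depend on the arms differing.

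**The case against.** A reader might infer that capture depends on the arm and that the safety comparison is therefore biased. The documents do not support that as a statement of fact.

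- The outcome comes from self-report questionnaires at the same times in both arms. Nothing says that events are collected at pharmacist visits.
- Glucometers and up to 4 × 50 = 200 strips are offered to participants in both arms, and a reading below 4.0 mmol/L counts without any cause. This may make the assumed share without a reading too high.
- Usual-care patients may also receive nurse counselling and dietitian referral.

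These points stand. What remains is indirect: patients seen every four to six weeks may recognise causes, or test, more often. That is plausible, but both its size and its direction are assumed.

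A reader might also infer that every assisted event with low glucose belongs to both categories. The recovery sentence rules that out, and most readers would take need for help as deciding the matter.

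The questionnaire is not shown, so it may ask about unexplained events. The gap is shown for the definition, not for the data actually collected.

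Finally, hypoglycaemia lies outside the main clinical parameters, and the major definition carries no cause condition. Both points limit the consequence. They do not close the gap: applied as written, the minor definition excludes a recognisable class of events.

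**Conclusion.** The concern holds as a defect in the outcome definition. Unassisted symptomatic events with no reading below 4.0 mmol/L and no known modifiable cause are counted in neither category, so the rule undercounts self-managed hypoglycaemia. That conclusion rests on the protocol's wording alone. The overlap is real but narrow.

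The figures of 3-25% uncounted and a 7-27% apparent excess in the collaborative arm rest wholly on the assumed inputs. They show what could happen, not what will. Differential capture by arm should be described as possible.

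The HbA1c comparison and the cost-effectiveness analysis, which uses HbA1c reduction, are untouched, and the gap does not reach major events. The change should be made because it is cheap and concerns a safety outcome; the trial's main conclusion does not hang on it.

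**What to change.** Keep the protocol's own glucose threshold and help criterion, and reconcile the outcome definitions under Clinical Outcomes as follows.

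1. Every reported event falls in exactly one category, with need for another person's help separating major from minor.
2. A known precipitating cause is no longer a condition for counting. It is recorded as a separate descriptive item, asked identically in both arms.
3. Glucose-confirmed and symptom-only events are reported separately by arm.

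This is a change to what is counted, not to clinical management. The cost is a rewording of the definition and one questionnaire item.

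The downside is that some non-specific symptoms will be counted, and not necessarily equally in both arms. The change does not remove bias from self-report, since counselled patients may also report more symptoms. The separate reporting in item 3 makes any such imbalance visible.
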